Title: HCC Screening using DNA methylation Changes in ctDNA

ClinicalTrials.gov Identifier: NCT03483922

Date: January 11, 2022

Clinical study design

Study protocol was approved by IRB board of icddr,b (Dhaka, Bangladesh) study protocol PR-18025. 402 participants were recruited from the Dhaka area to the study included 49 healthy controls, 51 Chronic hepatitis B patients and 303 HCC patients from stages 0 to D (HCC O n=2, HCCA n=32, HCC B n=86, HCC C n=106, HCC D n=77 (See Table 2 for demographics). The age of the healthy control and the chronic Hepatitis B (CHB) groups were significantly younger 27 than the HCC group, however there was no significant effect of age on HCC prediction by DNA

methylation as determined by a logistic regression in either the HCC or control groups. However, in the CHB group age had a significant effect on HCC prediction by the DNA methylation test, consistent with the idea of a higher probability for older patients with chronic hepatitis to convert to HCC. There were no differences between the groups in the sex distribution. However, there was a somewhat significant lower alcohol use and higher fraction of smokers in the HCC groups (Table 2). HCC staging was diagnosed according to EASL–EORTC Clinical Practice Guidelines: Management of hepatocellular carcinoma. Hepatitis B diagnosis was confirmed using AASLD practice guideline for chronic Hepatitis B

(https://www.aasld.org/publications/practice-guidelines). All participants were properly informed about the study and have signed the informed consent form approved by the icddr,b IRB. Inclusions criteria were participants of either sex 18 to 70 years of age, confirmed diagnosis of HCC using EASL-EORTC guidelines and chronic hepatitis B using AASLD guidelines, nonmetastatic

liver cancer, Hepatitis B surface antigen positive by ELISA and persistence of > 6 months. Exclusion criteria were unwilling or unable to provide informed consent, unwilling or unable to comply with requirements of protocol, participation in a different clinical trial investigating a vaccine, drug, medical device or medicinal procedure less than 4 weeks preceding the current study, planned participation in another clinical trial during present study period, known case of cirrhosis, any other known inflammatory disease (bacterial or viral infection with the exception of hepatitis B or C), known case of diabetes, asthma, autoimmune disease, any other diagnosed cancer, for healthy controls any known inflammatory or infectious disease including Hepatitis B and Hepatitis C and any diagnosis of chronic disease, cancer medication use or drugs of abuse. Patients were assigned an ID that was kept confidential according to

hospital regulations and identity was revealed only to approved hospital personnel. Participants provided consent for DNA methylation biomarker research. Blood sample collection ad plasma separation was performed at icddr,b in Dhaka Bangladesh and was then shipped to HKG epitherapeutics for further analysis. The HKG epitherapeutics lab team was blinded on the identity of the samples throughout the lab analytic procedures. Data was then analyzed in Montreal and shared with icddr,b who provided the results to the respective clinical personnel.

Blood was collected in 9-ml tubes containing K3-EDTA and processed within 1 h. Plasma and peripheral blood monocyte separation was performed according to GE Healthcare Cat No 71=7167-00 protocol. Plasma was frozen and shipped. Plasma samples (1 ml) were thawed, and DNA was extracted by previously described guanidine isothiocyanate method[43] and binding to silica magnetic beads followed by 80% ethanol washes and water elution.

Multiplexed Targeted DNA methylation Illumina amplicon sequencing

Bisulfate conversion was performed using EZ-96 DNA Methylation MagPrep (D5041, Zymo Research) followed by two rounds of polymerase chain reaction. For the first round we used primers that included an anchoring sequence and sequences targeting cg02012576 (CHFR), cg03768777 (VASH2), cg05739190 (CCNJ), cg24804544 (GRID2IP) and cg14126493 (F12) using Bio-Rad C1000 Touch Thermal Cycler (Bio-Rad Laboratories, CA, USA) (the primers are available upon request). 5 microliters of the first PCR reaction were subjected to a second round of PCR amplification using primers containing indexes for barcoding the samples (the primers are available upon request). PCR products were pooled, and the pooled library was then purified twice using AMPure XP Beads (Beckman Coulter Life Sciences, CA, USA) and quantified by RealTime PCR using NEBNext® Library Quant Kit for Illumina (New England Biolabs, MA, USA).

Sequencing was performed on the Illumina platform using MiSeq Reagent Nano Kit V2 (Illumina, CA, USA).

Statistical Analysis Plan

Significant difference from the control group was tested by Kruskal-Wallis non-parametric one-way ANOVA and was adjusted by Dunn's multiple comparisons test. The two HCC stage O samples were included for statistics in the HCC A group. ROC was computed using the ROC test in GraphPad.

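### The non-significant age check in 49 healthy controls has low, unreported power and does not show that age leaves specificity against healthy controls unaffected

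*Combined protocol and SAP*

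**What the plan says.** The Clinical study design section describes "49 healthy controls, 51 Chronic hepatitis B patients and 303 HCC patients", with eligibility for "participants of either sex 18 to 70 years of age". It then reports an age imbalance: "The age of the healthy control and the chronic Hepatitis B (CHB) groups were significantly younger" than the HCC group. In the same sentence it offers reassurance: "there was no significant effect of age on HCC prediction by DNA". The basis given is a logistic regression run within the HCC group and within the controls. It next reports that "in the CHB group age had a significant effect on HCC prediction by the DNA methylation test", and links this to older hepatitis patients being more likely to convert to HCC.

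For the age regressions the text gives no odds ratio, confidence interval, p-value or number of positive calls. The Statistical Analysis Plan section lists two analyses. In the first, "Significant difference from the control group was tested by Kruskal-Wallis non-parametric one-way ANOVA", with Dunn's adjustment. In the second, "ROC was computed using the ROC test in GraphPad". Neither has an age term, age matching or age strata.

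**The concern.** Cases are older than healthy controls. If the methylation score rises with age in people without cancer, part of the separation between HCC and healthy controls is an age difference, and specificity at the ages of the HCC patients is lower than in the younger controls studied. The non-significant regression is the only protection offered against this for the HCC-versus-healthy comparison.

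A non-significant result protects only if the test could have detected an effect that matters. Specificity depends on the control group alone. There the outcome appears to be a positive or negative call in 49 people, and the information about age comes mainly from however many of them were called positive. That number is not reported.

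**Working it through.** The documents state no power or effect size for this check, so there is no figure of theirs to reproduce.

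**Inputs from the documents.** Healthy controls n = 49, CHB n = 51, HCC n = 303.

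**Assumptions, not in the documents.** Two-sided alpha 0.05; logistic regression of a binary call on normally distributed age; false-positive rate p from 2% to 30%; odds ratio (OR) of 2 or 3 per within-group SD of age; age gap of 1 to 2 control-group SDs (the size of the gap is not in the text, and Table 2 is not available here).

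**Step 1: power in the 49 controls.** Power = Φ(√(n·p·(1−p))·ln OR − 1.96). At p = 10%, √(49 × 0.1 × 0.9) = 2.1. For OR 2 this gives Φ(2.1 × 0.693 − 1.96) = Φ(−0.504) = 31%. For OR 3 it gives Φ(2.1 × 1.099 − 1.96) = Φ(0.347) = 64%.

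**Step 2: what a perfectly null estimate would exclude.** With an estimated OR of 1, the upper 95% limit is exp(1.96/√(n·p·(1−p))). At p = 10% this is exp(1.96/2.1) = 2.5.

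| Assumed false-positive rate | Expected positives (49·p) | Power, OR 2 | Power, OR 3 | OR detectable with 80% power | Upper limit if estimate = 1 |
|---|---|---|---|---|---|
| 2% | 1.0 | 10% | 19% | 17.4 | 7.4 |
| 5% | 2.5 | 18% | 39% | 6.3 | 3.6 |
| 10% | 4.9 | 31% | 64% | 3.8 | 2.5 |
| 20% | 9.8 | 49% | 87% | 2.7 | 2.0 |
| 30% | 14.7 | 60% | 94% | 2.4 | 1.8 |

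At the most favourable rate possible (50%), power for OR 2 is 68%.

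**Step 3: simulation check** (1,500 samples of 49 per cell). For OR 2, likelihood-ratio power at the five rates was 10%, 20%, 29%, 48% and 55%; Wald power was 1%, 9%, 20%, 43% and 49%. For OR 3, likelihood-ratio power was 19%, 37%, 56%, 80% and 86%. At a 2% rate about 36% of samples had no positive call, so no model could be fitted.

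**Step 4: what an undetected effect could do.** With OR 2 per SD and a gap of 1 to 2 SD, a specificity of 95% in the controls becomes 91% to 84% at HCC-like ages, and 90% becomes 82% to 71%. For the AUC, take a binormal score with correlation r = 0.3 with age and an observed AUC of 0.90, so d = √2 × 1.282 = 1.812. The age-aligned AUC is Φ((d − r·gap)/√2): Φ(1.512/1.414) = 0.86 for a gap of 1 SD and Φ(1.212/1.414) = 0.80 for 2 SD. These figures illustrate possible size; they are not estimates for this test.

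**Step 5: the HCC group.** With n = 303 and OR 2, the Step 1 formula gives 75% power if 5% of HCC patients are misclassified, 95% if 10% are, and over 99% if 20% are. That check is far better powered, but it concerns sensitivity.

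**The case against.** The strongest reply is that the power figures depend on a false-positive rate the documents do not give. A reader might infer that the check has almost no power. That would hold only at rates of about 5% or less with an OR of 2 or lower. At 20% to 30% the check has about 80% to 94% power for an OR of 3. This stands: the supportable description is low and unreported power for a moderate effect.

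The HCC null is also real evidence. One might argue that tumour DNA would mask any age effect in HCC patients, but that presumes near-complete sensitivity. No sensitivity is stated, and 34 HCC patients (2 + 32) are stage 0 or A. The null counts for sensitivity and part of the AUC, but it cannot speak to specificity.

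The CHB result cuts both ways. It shows that age can move the call in a non-cancer group. It also shows that about 50 participants can suffice in some settings, although the CHB positive rate is unknown. The document's explanation, conversion risk, may not apply to healthy controls, who must be free of hepatitis B. So the CHB result does not establish an age effect in healthy controls.

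The binary call at one cut-off is likewise inferred from the use of logistic regression; no cut-off is stated. Finally, the document discloses the imbalance and says only that no significant effect was found. It does not say that age is ruled out, but the placing of the sentence invites that reading.

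**Conclusion.** The concern holds in limited form. The imbalance is admitted, the sole answer is a non-significant test reported without an estimate or interval, and the SAP has nothing that accounts for age. Across assumed false-positive rates of 2% to 30%, power for a doubling of false-positive odds per SD stays at about 60% or below. Up to a rate of about 20%, even a null estimate would leave that doubling inside the 95% interval. The check therefore does not show that specificity against healthy controls is unaffected by age.

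A reader might go further and infer that age does inflate the AUC or specificity. The documents do not support that: they give neither the size of the age gap nor any slope of the score on age in healthy controls. The point is that an age effect is not excluded. It concerns HCC versus healthy controls, not HCC versus CHB.

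**What to change.** - In the 49 healthy controls, regress the continuous methylation score on age. Report the slope with its 95% CI, scaled to the age difference between controls and HCC patients. The continuous score generally carries more information than a call, but the gain depends on the model: about 72% power under a logistic latent score with OR 2 per SD, and 56% at a correlation of 0.3. The interval matters more than the p-value.
- For the existing logistic check, report the age odds ratio with its 95% CI and the number of false positives.
- Add to the SAP an HCC-versus-healthy ROC with age adjustment, or one restricted to the overlapping age range if Table 2 shows a usable overlap.
- Replace the statement of no significant age effect with one saying that an age effect is not excluded, unless the interval rules out a shift large enough to matter.

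The cost is re-analysis of data already held, plus wording. The age-restricted ROC will have a wider interval, and the AUC may be slightly less favourable.

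### The ROC analysis ignores age, although CHB patients are younger than HCC patients and age affects their test result; if CHB patients are the negatives, accuracy at HCC ages may be overstated

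*Combined protocol and SAP*

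**What the plan says.** The Clinical study design section gives the groups as "49 healthy controls, 51 Chronic hepatitis B patients and 303 HCC patients". It then makes three statements about age:

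- **Imbalance with HCC.** "The age of the healthy control and the chronic Hepatitis B (CHB) groups were significantly younger" than the HCC group.
- **HCC and healthy controls.** No significant age effect was found on prediction by DNA "methylation as determined by a logistic regression in either the HCC or control groups".
- **CHB.** By contrast, "in the CHB group age had a significant effect on HCC prediction by the DNA methylation test". The document calls this "consistent with the idea of a higher probability for older patients with chronic hepatitis to convert to HCC".

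The size of the age gap is not in the text, which points the reader elsewhere: "See Table 2 for demographics". That table is not in the supplied text and may report the gap.

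The accuracy analysis in the Statistical Analysis Plan is one sentence: "ROC was computed using the ROC test in GraphPad". It has no covariate, matching, stratification or sensitivity analysis, and it defines neither positives nor negatives. The other analysis in that section, Kruskal-Wallis with Dunn's test, has no age term either.

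**The concern.** Within CHB, age is related to the test result. Between CHB and HCC, age differs. A plain HCC-versus-CHB ROC therefore mixes the effect of cancer with the effect of being older. If older CHB patients read as more HCC-like, a younger CHB group yields fewer false positives than CHB patients of HCC age would.

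The title is "HCC Screening using DNA methylation Changes in ctDNA", and CHB is the only at-risk group without cancer that was enrolled. HCC versus CHB is thus the comparison closest to the intended use. Specificity in the 51 recruited CHB patients is not wrong for those patients. It may not carry over to older ones, and the document's own regression gives the reason to doubt that it does.

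**Working it through.** The documents state no AUC, sensitivity, specificity, cut-off or age coefficient, so there is no figure to reproduce. What follows is an illustration of size.

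**From the document:** 51 CHB and 303 HCC patients; a significant age difference; a significant age effect on the test in CHB, with an upward direction implied by the conversion explanation.

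**Assumed:** CHB patients are negatives at a fixed cut-off; ages are normal; 5/51 or 10/51 CHB patients test positive; significance means two-sided 5%.

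1. *Age gap.* The smallest gap significant for 51 v 303 is 1.96 × √(1/51 + 1/303) = 0.297 SD. The upper value, 1.0 SD, is assumed.
2. *Age effect.* The smallest significant odds ratio per SD of age (score approximation) is exp(1.96/√(51·p·(1−p))). With p = 5/51 this is 2.52; with p = 10/51 it is 2.00. A Wald threshold gives 3.06 and 2.22, so the score version is the milder. Half the log odds ratio is also shown, in case the true effect is weaker than a just-significant estimate.
3. *Standardised specificity* = 1 − mean of logistic(a + b(z + g)), with z ~ N(0,1), g the age gap, b the log odds ratio, and a set so that the mean at g = 0 equals 5/51 or 10/51.

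| Scenario, g from 0.297 to 1.0 | Crude 90.2% (46/51) | Crude 80.4% (41/51) |
|---|---|---|
| Full b | 87.7% to 80.0% | 77.2% to 68.5% |
| Half b | 88.9% to 85.4% | 78.8% to 74.5% |
| Opposite sign, full b | 92.2% to 95.6% | 83.2% to 88.7% |

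For an upward effect the falls are 2.5–10.2 and 3.2–11.9 points (full b), or 1.3–4.8 and 1.6–5.9 points (half b).

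4. *Sampling error for comparison.* The exact (Clopper-Pearson) 95% intervals are 78.6–96.7% for 46/51 and 66.9–90.2% for 41/51. Every value in the table lies inside the interval for its column.

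**Second model, for AUC.** Take an equal-variance binormal score with within-CHB age–score correlation r. The smallest r significant with n = 51 is t/√(49 + t²) with t = 2.010, which is 0.276; this is a linear stand-in for the reported logistic regression. The age-aligned AUC is Φ(z(AUC) − r·g/√2). From an assumed crude AUC of 0.90 it becomes 0.88, 0.86, 0.84 and 0.81 for assumed gaps of 0.5, 1, 1.5 and 2 SD. With no cancer signal at all, age alone would give an AUC of 0.54 to 0.65 over the same gaps.

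**Healthy controls.** With 49 controls, the approximate power to detect r = 0.276 is Φ(atanh(0.276)·√46 − 1.96) = 48%. The non-significant result there is weak reassurance, but it is not evidence of bias.

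**The case against.** The strongest objection is that the CHB argument needs CHB patients among the ROC negatives, and the plan never says they are. The only comparator that the Statistical Analysis Plan names is the control group, and the design section uses that term as distinct from CHB. That wording belongs to the Kruskal-Wallis sentence and does not settle the ROC. If the negatives are healthy controls only, the CHB argument does not apply; bias is then possible but not shown. On this view the more basic gap is that the ROC groups are undefined. This stands as a condition on the conclusion.

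Second, age was examined and the unfavourable CHB result was disclosed. That is true, but disclosing the effect does not carry it into an AUC or a specificity.

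Third, older CHB patients who test positive may be converting to HCC. No follow-up is described that could show this, so against the recorded diagnosis they are false positives.

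Fourth, the sizes rest on assumed inputs, no coefficient confirms the direction, and the shifts lie within sampling error. All of this stands. It limits what can be said about size but does not make an unadjusted HCC-versus-CHB ROC a sound basis for statements about older patients.

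Fifth, the remedy may be imprecise. An age-restricted analysis could leave few CHB patients, and standardisation extrapolates if few of them reach HCC ages. This also stands, as a cost.

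**Conclusion.** The concern holds and should be fixed; confidence is medium. The document reports both the age imbalance and the CHB age effect, and the ROC plan handles neither. Overstatement at HCC ages follows if two conditions are met: CHB patients serve as negatives, and older CHB patients test positive more often. The plan leaves the first open; its conversion explanation implies the second.

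Under the assumptions above, the fall in CHB specificity could be as small as 1.3 points or as large as about 10 to 12. An effect in the other direction would raise it by 2.0 to 8.3 points. Only the sponsor's data can settle which applies.

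**What to change.** In the Statistical Analysis Plan:

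1. Report ROC and specificity separately for HCC versus healthy controls and HCC versus CHB, each with 95% confidence intervals. This also settles who the negatives are.
2. For HCC versus CHB, add one age-handling sensitivity analysis: an age-adjusted ROC, or CHB specificity standardised to, or restricted to, the age range shared with the HCC cases. CHB results stratified by age are an acceptable simpler form. Label it post hoc, because the text describes completed work.
3. Count test-positive CHB participants as false positives in this analysis.

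The Kruskal-Wallis and Dunn analysis need not change.

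The cost is SAP wording and a re-run on data already collected. Age restriction would leave fewer than 51 CHB patients. If, say, 25 remained and 22 were negative, the exact 95% interval would be 68.8–97.5%, about 29 points wide against 18 for 46/51. The reported accuracy may also be lower.

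### The SAP tests only for difference from the control group, most likely hepatitis-free healthy controls. It names no HCC versus chronic hepatitis B comparison and gives the ROC no comparator.

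*Combined protocol and SAP*

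**What the plan says.** The Statistical Analysis Plan has three sentences. The first states the test, "Significant difference from the control group was tested by Kruskal-Wallis non-parametric one-way ANOVA", and says that it "was adjusted by Dunn's multiple comparisons test". The second merges the two stage 0 samples into HCC A. The third is "ROC was computed using the ROC test in GraphPad". It names no positive class and no negative class.

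The SAP does not define the control group. The Clinical study design section points to its meaning in three places:

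- Recruitment is listed as "49 healthy controls, 51 Chronic hepatitis B patients and 303 HCC patients from stages 0 to D", so healthy controls and CHB are separate groups.
- There was no significant age effect on prediction by DNA "methylation as determined by a logistic regression in either the HCC or control groups", whereas "in the CHB group age had a significant effect on HCC prediction by the DNA methylation test". Here the bare word control excludes CHB.
- The exclusion criteria include "for healthy controls any known inflammatory or infectious disease including Hepatitis B and Hepatitis C and any diagnosis of chronic disease".

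On age, the same section says "The age of the healthy control and the chronic Hepatitis B (CHB) groups were significantly younger" than the HCC group. Nowhere do the documents state an HCC versus CHB test, ROC or specificity estimate.

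**The concern.** The title presents the assay as HCC screening, and hepatitis B surface antigen positivity is among the inclusion criteria. Whether the assay tells HCC from chronic hepatitis B is therefore a central question. Healthy controls without hepatitis, inflammatory disease or chronic disease differ from HCC patients in more than cancer. A methylation marker that responds only to hepatitis or liver damage would separate HCC from these controls and pass the stated test.

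Readers might look at whether CHB also differs from control. Setting one significant result beside one non-significant result is not a test of the difference between the two groups. The ROC does not settle the matter either, because the same sentence would cover an AUC against healthy controls, against CHB or against both pooled.

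**Working it through.** **Plan's own figures.** The documents give no alpha, effect size, power or AUC, so there is no design figure to reproduce. The stage counts agree: 2 + 32 + 86 + 106 + 77 = 303. The groups sum to 49 + 51 + 303 = 403 against the stated 402, which does not affect this point.

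**Contrasts under the stated rule.** With stage 0 merged into A there are six groups: control 49, CHB 51, HCC 0/A 34, B 86, C 106 and D 77. Comparisons against control number 6 − 1 = 5, none of them HCC versus CHB. All pairs would be 6 × 5 / 2 = 15, of which four are an HCC stage versus CHB. The SAP states only the against-control form.

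**What that rule reports for a marker with no cancer information.** Assumptions: normal scores; the same shift d (in SD) in CHB and every HCC stage; Dunn's z = (difference in mean ranks) / √[N(N+1)/12 × (1/nᵢ + 1/nⱼ)]; Bonferroni ×5 at two-sided 0.05; 10,000 simulated trials per row.

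| d | Any HCC stage v control | CHB v control | HCC stage significant, CHB not | Same, Dunn only after significant Kruskal-Wallis | Any stage v CHB, direct (×4) |
|---|---|---|---|---|---|
| 0.3 | 33.9% | 12.9% | 24.2% | 13.8% | 4.1% |
| 0.5 | 78.1% | 42.0% | 38.4% | 27.1% | 3.3% |
| 0.8 | 99.4% | 88.5% | 11.0% | 10.2% | 3.2% |
| 1.0 | 100.0% | 98.3% | 1.7% | 1.6% | 3.4% |

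The misleading pattern arises partly because HCC has four chances to reach significance and CHB has one. Most stages are also larger than CHB. For CHB, √(1/49 + 1/51) = 0.200; for stage C, √(1/49 + 1/106) = 0.173. The same shift therefore gives a z about 0.200 / 0.173 ≈ 1.16 times larger in stage C. The direct contrasts stay at 3–4%.

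**What the unspecified ROC allows.** Pooled AUC = (49 × AUC against healthy + 51 × AUC against CHB) / 100. Assume 0.95 against healthy controls:

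- AUC against CHB of 0.60: (49 × 0.95 + 51 × 0.60) / 100 = 0.77.
- AUC against CHB of 0.90: (49 × 0.95 + 51 × 0.90) / 100 = 0.92.

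On these assumptions, one sentence would permit reported AUCs from 0.60 to 0.95.

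**Age.** In 3,000 runs per setting, 51 CHB were compared with 303 HCC on a marker that depends on age only, with a common slope. If HCC patients are 1 SD of age older and the marker-age correlation is 0.3 (both assumed), an unadjusted Wilcoxon test rejects in 49% and a rank ANCOVA with age in 5%. Over age gaps of 0.5–1.5 SD and correlations of 0.2–0.4, the unadjusted rate runs from 10% to 97% and the adjusted rate from 4% to 6%.

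**Whether the enrolled groups can support the missing comparison.** The Hanley–McNeil variance is [A(1−A) + (n₁−1)(Q₁−A²) + (n₀−1)(Q₂−A²)] / (n₁n₀), with Q₁ = A/(2−A) and Q₂ = 2A²/(1+A). At an assumed A = 0.80, Q₁ = 0.667 and Q₂ = 0.711:

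- All HCC v CHB (303, 51): (0.160 + 8.053 + 3.556) / 15,453 = 0.000762; SE 0.0276; 95% half-width 0.054.
- Stage 0/A v CHB (34, 51): (0.160 + 0.880 + 3.556) / 1,734 = 0.00265; SE 0.0515; 95% half-width 0.101.

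Specificity of 46/51 = 90% in CHB would have an exact 95% CI of 79% to 97%.

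**The case against.** The strongest reply is that HCC versus CHB is unstated rather than ruled out. The control group is undefined, Kruskal-Wallis is an omnibus test, Dunn's procedure can be run on all pairs, and the ROC may have used CHB. All of that is true. The finding is that the plan does not specify the comparison, not that nobody carried it out. The only form the SAP states is against control. If control did include CHB, the plan would still have no separate HCC versus CHB comparison.

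Second, detecting a real shift from healthy controls is power, not error. This is also right. The 34% to 100% figures mislead only if read as evidence of a cancer signal. The more telling column is the misleading pattern, which peaks at 38% among the shifts tried and falls to 2% at 1.0 SD, because CHB then usually separates from control too. All of these figures assume one normally distributed marker with equal shifts. The assay targets five CpG sites, and the documents do not say how they are combined.

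Third, the age figures assume a common slope, whereas the Clinical study design section reports an age effect in CHB and no significant one in HCC. With r = 0.3 in CHB only, a 1 SD age gap and no group difference at the CHB mean age, the unadjusted test rejects in about 5%. That result depends on the centring, and non-significance in HCC does not establish a zero slope. The reported age effect also concerns HCC prediction rather than raw marker level. The 10% to 97% range is therefore illustrative. It shows why age must be handled and does not estimate the bias in this study.

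Last, the text describes recruitment as complete, so new contrasts cannot be prespecified. That limits what they can claim but does not remove the need for them.

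**Conclusion.** The concern holds. That the control group means healthy controls is an inference, but a strong one. On that reading the SAP tests five contrasts against hepatitis-free controls and states no test or ROC that would show whether the assay distinguishes HCC from chronic hepatitis B. Under assumed hepatitis-only shifts of 0.3 to 1.0 SD, the plan would usually or often flag HCC stages against control. Between 2% and 38% of trials would show an HCC stage significant with CHB not, in the absence of any cancer information. Confidence is high for the missing specification. The sizes rest on the stated assumptions, and the age range most of all. The plan should be corrected before any claim of cancer detection is based on it.

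**What to change.** 1. Define the control group in the SAP.
2. Name HCC versus CHB as Dunn contrasts by stage, with 0/A merged as already planned. Add an overall HCC versus CHB rank contrast, defined explicitly because pooled HCC is not one of the six groups. Base any claim of cancer detection on these. The healthy-control contrasts can stay.
3. State the ROC classes. Report AUC with confidence intervals separately for HCC versus CHB and HCC versus healthy controls, and show specificity in the 51 CHB patients on its own, not only pooled.
4. Add an age-adjusted HCC versus CHB analysis, checking age overlap and an age-by-group interaction.
5. Label all of these as added after recruitment.

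The cost is SAP wording and some further analysis of samples in hand. Going from 5 to 10 contrasts raises the two-sided Bonferroni critical value from 2.58 (0.05/5) to 2.81 (0.05/10). With 10 contrasts and an assumed HCC–CHB difference of 0.7 SD, simulated power is 0.53 for stage 0/A, 0.81 for B, 0.86 for C, 0.79 for D and 0.94 overall. Stage 0/A is the weak point, so its estimate should be reported with its interval and not judged on significance alone. AUC and specificity against CHB will probably be less favourable than against healthy controls.

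### Dunn's adjustment is valid, but Holm's step-down on the same five p-values keeps the 5% familywise bound and can give stage 0/A more power, depending on effect sizes the documents do not state

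*Combined protocol and SAP*

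**What the plan says.** The Statistical Analysis Plan has three sentences, and two bear on this point. The first sets the test, "Significant difference from the control group was tested by Kruskal-Wallis non-parametric one-way ANOVA", and the multiplicity step, "ANOVA and was adjusted by Dunn's multiple comparisons test". The second fixes the grouping: "The two HCC stage O samples were included for statistics in the HCC A group".

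The group sizes are under Clinical study design: "49 healthy controls, 51 Chronic hepatitis B patients", and for the cancer stages "HCC O n=2, HCCA n=32, HCC B n=86, HCC C n=106, HCC D n=77".

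The plan does not state a significance level, sidedness, the number of comparisons, an effect size or a power target. It names no step-down procedure.

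**The concern.** A single-step correction charges every comparison for the whole family, whatever happens to the others. If stages B, C and D have already been declared different from control, at most two true null hypotheses remain (CHB and 0/A), yet each is still tested as if there were five. A step-down method uses that information without exceeding the same familywise bound.

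Any loss falls on the comparisons that are small or weakly separated. Stage 0/A is the smallest group, with 34 patients against 269 in B to D. In a study titled as screening, early disease against control is a comparison readers will look for. At stake is some avoidable loss of power there. The validity of the analysis is not in question.

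**Working it through.** **Inputs from the documents.** Control 49, CHB 51, stage 0/A 2 + 32 = 34, B 86, C 106, D 77. The stages sum to 303. All groups sum to 49 + 51 + 303 = 403, whereas the text gives 402; this does not affect the point. Six groups give five comparisons with control.

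**Assumptions.** Two-sided familywise level of 5%; Dunn's test in its standard single-step form; unit-SD normal outcomes with a range of shifts. The documents have no power or sample-size figure to reproduce.

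**Step 1: thresholds.** Bonferroni: 0.05/5 = 0.0100 for every comparison. Holm, from smallest to largest p-value: 0.05/5, 0.05/4, 0.05/3, 0.05/2, 0.05/1 = 0.0100, 0.0125, 0.0167, 0.0250, 0.0500. Holm stops at the first p-value that fails. No Holm threshold is below 0.0100, so every Bonferroni rejection is also a Holm rejection. Both methods keep the familywise error at or below 5% under any dependence, provided each pairwise p-value is valid under its own null.

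**Step 2: closed form for 0/A against control.** If B, C and D are rejected first and CHB is not, 0/A is tested at 0.025 instead of 0.01. For a shift of d SD the noncentrality is d/√(1/49 + 1/34) = d × √(1666/83) = 4.480d. Power is about Φ(4.480d − z), with z = 2.576 at 1% and 2.241 at 2.5%. This treats the comparison as a two-group normal test and ignores joint ranking.

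| d | power at 1% | power at 2.5% |
|---|---|---|
| 0.5 | 37% | 50% |
| 0.7 | 71% | 82% |
| 0.8 | 84% | 91% |
| 1.0 | 97% | 99% |
| 1.2 | 99.7% | 99.9% |

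The shift detectable with 80% power falls from (2.576 + 0.842)/4.480 = 0.76 SD to (2.241 + 0.842)/4.480 = 0.69 SD.

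**Step 3: simulation of the planned test.** All observations are ranked jointly. Dunn's z is the difference in mean ranks divided by √(N(N+1)/12 × (1/nᵢ + 1/n₀)). Bonferroni and Holm are applied to the same p-values, with 20,000 runs per scenario and CHB equal to control.

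| Pattern | 0/A shift (SD) | Dunn/Bonferroni | Holm |
|---|---|---|---|
| Same shift in all HCC stages | 0.5 | 33% | 41% |
| | 0.7 | 66% | 76% |
| | 0.8 | 79% | 87% |
| | 1.0 | 95% | 97% |
| Rising by stage (d, 1.5d, 2d, 2.5d) | 0.5 | 25% | 39% |
| | 0.7 | 47% | 63% |
| | 1.0 | 74% | 87% |
| | 1.5 | 92% | 98% |
| B to D at 3 SD | 0.5 | 0% | 0.2% |
| | 1.0 | 10% | 28% |
| | 2.0 | 100% | 100% |
| Only 0/A differs | 0.8 | 78.9% | 79.0% |

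The gain runs from zero to about 18 points.

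**Step 4: error control.** With no group different, the simulated familywise error is 4.0% under both methods. When some groups differ, it is at most 3.4% under Holm. It does rise relative to Bonferroni: with all HCC stages at 0.7 SD and CHB null, from 0.5% to 2.3%.

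**The case against.** The strongest reply is that nothing is wrong. Dunn's test is a recognised procedure that controls familywise error, and the plan is free to use it. That stands: the point concerns efficiency only. It is still more than a matter of taste, because Holm cannot reject less than Bonferroni on the same p-values.

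Second, the gain rests on assumed effects. A 0.7 SD normal shift is an AUC of about Φ(0.7/√2) = 0.69. At 1.2 SD (AUC about 0.80), with B, C and D shifted by a further 0.2, 0.4 and 0.6 SD, 0/A power is 98% under Bonferroni and 99% under Holm. A marker good enough for screening may therefore gain little. This also stands, although with effects rising more steeply (d to 2.5d) the gain at 1.2 SD is 85% to 94%.

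Third, the document is written in the past tense, with recruitment and analysis described as done. A less strict adjustment chosen after the p-values are known is post hoc. That stands and shapes the fix. It also means that any saving in patient numbers has no use here.

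Fourth, Holm leaves a possibly larger loss in place. With effects rising by stage and 0/A at 0.8 SD, simulated power under joint ranking is 58% at the 1% threshold, against 84% for a two-group normal approximation at the same threshold. Holm lifts the 58% to 74% but leaves the ranking as it is. Nor does it touch the ROC analysis, which is the part of the plan that bears on screening accuracy.

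A reader might infer that stages B to D are sure to be significant, or that the plan will report early disease as no different from control when it is different. The documents contain no methylation results and support neither inference.

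**Conclusion.** The point holds as a conditional efficiency gain. At an assumed two-sided familywise 5%, the planned adjustment holds each of five comparisons to 1%. Holm on the same Dunn p-values keeps the 5% bound and is never less powerful.

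For stage 0/A the gain is roughly 8 to 18 points if B to D also differ from control and the 0/A shift is moderate: about 0.5 to 0.8 SD, or up to about 1.2 SD if effects rise by stage. It is near zero in three situations: few other comparisons are rejected; 0/A separates so strongly that both methods have almost full power; or B to D lie so far out that joint ranking leaves 0/A little power under either method.

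It is tempting to say flatly that Holm gives early-stage patients clearly more power, or that Dunn's test is a mistake. The first needs effect sizes that the documents do not give, and the second is untrue. That the adjustment is single-step also comes from the standard form of Dunn's test; the plan does not spell it out.

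**What to change.** Keep the Kruskal-Wallis test and Dunn's pairwise z-tests, so that the test producing the p-values stays specified, and change only the adjustment:

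> *The unadjusted Dunn p-values for the five comparisons with control (CHB, stage 0/A, B, C, D) are adjusted by Holm's step-down method at a two-sided familywise 5%.*

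This sentence also supplies the family of comparisons, the level and the sidedness, which the plan leaves unstated. If results had already been seen, report the Holm-adjusted p-values beside the planned Dunn-adjusted ones and label them post hoc.

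The cost is one sentence and a trivial calculation, with no new data. There are two drawbacks. Holm has no simple matching simultaneous confidence intervals, though the plan has none. The attained familywise error rises when some groups truly differ, but stays below 5%.
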